The annual rate of on-treatment moderate and severe exacerbations in the FF/VI treatment arm was 0.92 based on those subjects in the FF/VI arms from the FF/VI Phase IIIa program who can be classified as 'high risk' (unpublished data: studies HZC102871 and HZC102970) according to the most recent COPD guidelines [GOLD, 2013]. Based on these data, the exacerbation rate for FF/UMEC/VI in the current study is estimated to be 0.80 for purposes of sample size calculations, with the estimate for FF/VI being 12% higher (approximately 0.91) and the estimate for UMEC/VI being 15% higher (approximately 0.94). The co-primary endpoints will be controlled for multiplicity using the truncated Hochberg method [Dmitrienko, 2008]. In order to have 90% power to detect a 15% reduction in the annual rate of moderate and severe exacerbations in the FF/UMEC/VI arm compared with the UMEC/VI arm and a 12% reduction compared with the FF/VI arm, 4000 subjects will be randomized to each of the FF/UMEC/VI and FF/VI arms, along with 2000 subjects to the UMEC/VI arm. Calculations are based on a negative binomial regression and use a two-sided 1% significance level in order to satisfy regulatory requirements of substantial evidence of efficacy for a single study. For the multiplicity hierarchy, a 2-sided 5% risk associated with incorrectly rejecting the null hypothesis (significance level) is considered acceptable for this study. The estimate of the dispersion parameter for the negative binomial model is 0.75, which is similar to that seen with fluticasone propionate/salmeterol in the TORCH study [Calverley, 2007] and the dispersion in the FF/VI exacerbation program [Dransfield, 2013].

Subjects will be randomized in a 2:2:1 proportion to the FF/UMEC/VI, FF/VI and UMEC/VI arms, respectively. All randomized subjects (approximately 10,000 in total) are considered to be evaluable for the measurement of exacerbations, irrespective of whether they permanently discontinue from IP. Assuming a 38% screen failure rate, based on the FF/VI Phase III exacerbation program, it is estimated that approximately 16,000 subjects will be screened.

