### 8.3. Time to First COPD Moderate/Severe Exacerbation

#### 8.3.1. Planned Primary Statistical Analyses for Time to First On-treatment Moderate/Severe Exacerbation

Secondary Statistical Analyses
Endpoint

 
• Time to first on-treatment moderate/severe exacerbation
 

Model Specification

 
• Cox's proportional hazards model
 
• Terms in the model: 
 
• Response: time to first on-treatment, moderate/severe exacerbation
 
• Categorical: treatment group, gender, exacerbation history (<math>\leq 1</math>, <math>\geq 2</math> moderate/severe), smoking status (screening), geographical region
 
• Continuous: post-bronchodilator % predicted FEV1 (Screening)
 
 
 
• The 'exact' method will be used for handling ties. If the analysis will not run using the 'exact' method, then the 'Efron' method for handling ties will be used instead.
 
• Kaplan-Meier survivor functions will be obtained for each treatment group using PROC LIFETEST with a TIME statement.
 

Model Checking & Diagnostics

 
• Refer to Appendix 10: Model Checking and Diagnostics for Statistical Analysis
 

Model Results Presentation

 
• Hazard ratios and the percent reduction in risk for the pairwise treatment comparisons with associated 95% CIs and p-values will be presented.
 
• Both adjusted (accounting for the Hochberg multiplicity adjustment, see Section 11.9) and unadjusted p-values will be presented for the pairwise treatment comparisons of FF/UMEC/VI versus FF/VI and FF/UMEC/VI versus UMEC/VI. Only unadjusted p-values will be presented for the treatment comparison of UMEC/VI versus FF/VI. The probability of having a moderate/severe exacerbation, 95% CI and first quartile and median time to exacerbation for each treatment group will be presented.
 
• The Kaplan-Meier curves will be presented showing the probability of having an event over
 

time for each treatment group separately plotted on the same figure. This will be repeated displaying UMEC/VI and FF/VI only.
Example SAS Code

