
 
● Laboratory results, ECG results/findings and vital signs measurements collected as part of cardiovascular event reports will not be included in any tables, listings or any minimum/maximum post-baseline assessments.
 
	
Descriptive Summary Statistics	
Continuous Data	Refer to IDSL Statistical Principle 6.06.1
Categorical Data	N, n, frequency, %
p-value	

 
● Both adjusted and unadjusted p-values will be displayed on the primary analyses outputs for
 
	

Reporting Standards

the endpoints within the hierarchy (detailed in Section 11.9) and will be labeled 'Adjusted p-value' and 'Unadjusted p-value'
 

• All other p-values will be unadjusted and labeled purely as 'p-value'.

Time to event results

• For all time to event analyses, the first quartile and median time to event will be presented. If less than 25% of subjects experienced the event within a treatment group then the first quartile will be displayed as NA (not applicable) for that treatment. If less than 50% of subjects experienced the event within a treatment group then the median will be displayed as NA (not applicable) for that treatment.

Graphical Displays

• Refer to IDSL Statistical Principals 7.01 to 7.13.

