**Time to First On-treatment Exacerbation**

- The time to first on-treatment exacerbation will be calculated as exacerbation onset date of first on-treatment exacerbation – date of start of treatment + 1.
- Subjects will be represented from their Day 1 date to the start date of their first exacerbation or date of censoring. Subjects that have not experienced an on-treatment exacerbation are censored at the earliest of the date of their treatment stop date +1 day or the date of death.

COPD Exacerbations
Time to First Exacerbation Including Off-treatment data

 
The time to first exacerbation including off-treatment data will be calculated as exacerbation onset date of first exacerbation – date of start of treatment + 1.
 
Only exacerbations reported during the on-treatment and post-treatment study phases will be considered (see Section 11.3.3 for details of assigning study phase)
 
Subjects will be represented from their Day 1 date to the start date of their first exacerbation or date of censoring. Subjects that have not experienced an on or off-treatment exacerbation are censored at the earliest of (date of study conclusion or the date of death).
 

Time to First On-treatment Moderate/severe Exacerbation or Premature Study Treatment Discontinuation

 
The time to first on-treatment moderate/severe exacerbation will be calculated as exacerbation onset date of first on-treatment moderate/severe exacerbation – date of start of treatment + 1.
 
The time to study treatment discontinuation will be calculated as the date of premature study treatment discontinuation – date of start of treatment + 1.
 
The time to first on-treatment moderate/severe exacerbation or study treatment discontinuation is defined as the earliest of the time to first on-treatment moderate/severe exacerbation or time to premature study treatment discontinuation.
 
Subjects will be represented from their Day 1 date to the earliest of the event or censoring. Subjects who do not experience the event will be censored at the earliest of the date of their treatment stop date +1 day or the date of death.
 

Time to Each On-treatment Exacerbation

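### The SAP decides whether to show a median or first quartile from the crude share of subjects with an event, not from the Kaplan-Meier curve, so an estimable median could be reported as NA

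*SAP*

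**What the plan says.** SAP section 11.4.3, under time to event results, sets the scope: "For all time to event analyses, the first quartile and median time to event will be presented". It then gives two display conditions. For the first quartile: "If less than 25% of subjects experienced the event within a treatment group then the first quartile will be displayed as NA". For the median: "If less than 50% of subjects experienced the event within a treatment group then the median will be displayed as NA".

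For time to first moderate/severe exacerbation, SAP section 8.3.1 promises that the "first quartile and median time to exacerbation for each treatment group will be presented", and names the estimator: "Kaplan-Meier survivor functions will be obtained for each treatment group using PROC LIFETEST with a TIME statement". SAP section 11.5.3.1 gives the censoring rule: subjects with no on-treatment exacerbation "are censored at the earliest of the date of their treatment stop date +1 day or the date of death".

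The display condition counts subjects who experienced the event. Section 11.5.3.1 uses the same verb for observed events. Section 8.3.1 speaks of a probability when it means the estimated quantity. Neither document says that the Kaplan-Meier percentile decides the display, so a programmer following the text would use the crude proportion.

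**The concern.** A subject who stops treatment early without an event stays in the denominator of the crude share but leaves the Kaplan-Meier risk set. With any such censoring the crude share falls below the Kaplan-Meier probability; with none, the two agree. The rule therefore errs in one direction. It never displays a median that the curve has not reached, but it can withhold one that the curve has reached.

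At stake is a prespecified descriptive summary of a secondary endpoint, which also forms the second block of the testing hierarchy. A table could show NA beside a Kaplan-Meier figure that visibly crosses 50%. The issue has practical weight here because the planning rates put the dual-therapy arms very close to 50% at 52 weeks.

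**Working it through.** The documents state no crude event share, Kaplan-Meier probability or median, so there is no figure of the plan's own to reproduce on this point.

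**Inputs**
- Annual rates (protocol 8.2.1): "the exacerbation rate for FF/UMEC/VI in the current study is estimated to be 0.80"; FF/VI 0.80/0.88 = 0.909; UMEC/VI 0.80/0.85 = 0.941.
- Negative binomial dispersion k = 0.75 (protocol 8.2.1).
- Treatment for 52 weeks, τ = 364/365.25 = 0.9966 year (protocol 5.2).
- Proportion D stopping treatment by week 52: not given. Assumed 0% to 30%, with constant hazard, unrelated to exacerbation risk and equal in all arms.

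**Formulas** (the plan's negative binomial model with annual rate m)
- Kaplan-Meier event probability by time t: 1 − (1 + k·m·t)^(−1/k).
- Median: (2^k − 1)/(k·m). First quartile: ((4/3)^k − 1)/(k·m).
- Crude share: the integral from 0 to τ of m(1 + k·m·t)^(−1/k − 1)·exp(−h·t), with h = −ln(1 − D)/τ.

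**UMEC/VI worked through**
- k·m·τ = 0.75 × 0.941 × 0.9966 = 0.703; 1 − 1.703^(−1.333) = 50.8%.
- Median: 0.682/(0.75 × 0.941) = 0.966 year, about day 353.
- First quartile: 0.241/0.706 = 0.341 year, about day 125.

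**All arms**

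| | FF/UMEC/VI | FF/VI | UMEC/VI |
|---|---|---|---|
| Kaplan-Meier probability, day 364 | 46.5% | 49.9% | 50.8% |
| Median (day) | 415 | 365 | 353 |
| First quartile (day) | 147 | 129 | 125 |
| Crude share, D = 5% | 45.5% | 48.9% | 49.8% |
| Crude share, D = 10% | 44.5% | 47.9% | 48.8% |
| Crude share, D = 20% | 42.5% | 45.7% | 46.6% |
| Crude share, D = 30% | 40.4% | 43.5% | 44.4% |

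The UMEC/VI crude share drops below 50% once discontinuation exceeds about 4%. FF/VI misses 50% at day 364. At the late end of the Visit 7 window (364 + 6 + 1 = day 371) it reaches 1 − (1 + 0.75 × 0.909 × 371/365.25)^(−1.333), about 50.4%, so it could fall either way.

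**Sensitivity to dispersion.** For UMEC/VI at k = 0.84: 1 + 0.84 × 0.941 × 0.9966 = 1.788, and 1 − 1.788^(−1/0.84) = 49.9%. The median is then not reached by day 364, and both rules give NA.

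**Sensitivity to the rate.** At k = 0.75 and with follow-up to day 364 or a few days beyond, the expected median is estimable but blanked for rates of about 0.91 to 0.98 at 10% discontinuation and about 0.91 to 1.07 at 20%. The matching band for the first quartile at 20% is about 0.32 to 0.37, far below the moderate/severe planning rates.

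**The case against.** The strongest reply is that nothing inferential depends on this. The hierarchy tests use Cox hazard ratios and p-values, and section 8.3.1 also presents the event probability with its 95% CI and the Kaplan-Meier curves, from which a missing median can be read. That stands.

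It also stands that the example is narrow. It needs early discontinuation, for which the documents give no rate, and an event rate just above the 50% threshold. In the 0.60 and 0.70 rows of protocol Tables 5 and 6, the highest comparator rate is 0.70/0.85 = 0.824. That gives 47.3% by day 364, so both rules show NA. The 0.75 dispersion is itself only a planning estimate.

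A reader might infer more than the documents support:
- **That one arm would show a median and another NA only because more of its subjects stopped treatment.** The documents give no differential discontinuation. At equal discontinuation of 5% or more, the present rule shows NA in all three arms. The Kaplan-Meier rule would give the mixed display, and correctly so.
- **That first quartiles for this endpoint are lost as well.** Crude shares are about 40% or higher throughout, well above 25%.
- **That the same gap affects every time-to-event analysis.** The sensitivity analysis that includes off-treatment data censors at study conclusion or death, so stopping treatment does not by itself create the gap there.

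The sponsor may have meant the Kaplan-Meier criterion all along. The text does not say so, and clarifying it costs nothing.

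**Conclusion.** The rule, followed as written, could suppress a median that the Kaplan-Meier curve reaches. At the planning inputs the case at risk is UMEC/VI (50.8% by day 364, crude share 49.8% to 46.6% at 5% to 20% discontinuation). FF/VI is borderline, and FF/UMEC/VI is NA under either rule. The quartile half of the rule could matter only for rarer events.

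The mechanism is certain whenever subjects are censored before week 52. Whether it occurs in this trial rests on the assumed discontinuation and on planning values for rate and dispersion that put UMEC/VI less than one percentage point above the threshold. The documents do not support a claim that the median will be lost, nor any claim that bears on the trial's conclusions. This is a minor reporting fault.

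**What to change.** Replace the two display conditions in SAP section 11.4.3 with one sentence: *The first quartile (median) is displayed as NA only when the Kaplan-Meier estimate of event probability does not reach 25% (50%) during follow-up.*

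The cost is one sentence. PROC LIFETEST already produces the quantiles, and no analysis, table shell or sample size changes. Making the change before unblinding avoids a later decision about which medians to show.

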## 11.5. Appendix 5: Derived and Transformed Data

### 11.5.1. General

#### 11.5.1.1. Study Day

Study Day

 
• Calculated as the number of days from treatment start date:               
 
○ Reference date = missing → Study Day = missing
 
○ Reference date < treatment start date → Study Day = reference date – treatment start date
 
○ Reference date ≥ treatment start date → Study Day = reference date – treatment start date + 1
 
 
 

#### 11.5.1.2. Treatment Stop Date

Study Treatment Stop Date

 
• If the treatment stop date is missing, it will be imputed as follows:               
 
○ If any of Study Treatment Discontinuation Visit date, Visit 7 (Week 52) date, date of death are non-missing then the study treatment stop date will be imputed as the minimum of (Study Treatment Discontinuation Visit date, Visit 7 (Week 52) date, date of death, date that all study treatment containers were returned).
 
○ For all other subjects, the last recorded exposure start or stop date will be used.
 
 
 

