4.5.3. Lost to follow-up

If a subject fails to attend the clinic for a required study visit, the site should attempt to contact the subject and re-schedule the missed visit as soon as possible. The site should also counsel the subject on the importance of maintaining the assigned visit schedule and ascertain whether or not the subject wishes to and/or should continue in the study based on previous non-compliance. In cases where the subject does not return for the rescheduled visit or cannot be reached to reschedule the missed visit, the site should make every effort to regain contact with the subject (3 telephone calls and if necessary a certified letter to the subject's last known mailing address) so that they can appropriately be withdrawn from the study. These contact attempts should be documented in the subject's medical record. If the subject continues to be unreachable, only then will he/she be considered to have withdrawn from the study with a primary reason of "Lost to Follow-up". For all other subjects withdrawing from the study, an alternative reason for

discontinuation should be recorded in the eCRF. Every effort should be made to collect survival status (whether the subject is still alive).

Note: If contact is lost with the subject, only the specific additional actions as clearly outlined in each subject's Informed Consent form (e.g. attempt contact with subject's listed contact and/or a primary care physician; request access to the subject's medical record) should be attempted to collect survival status.

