**11.3.2. All Cause Mortality**

For the summaries and analyses of the efficacy endpoint of all cause mortality, treatment phases will be defined as described in the table below after any imputation of partial death dates as described in Section 11.6.1:

Pre-treatment	Death Date < Treatment Start Date (i.e. subject did not start study treatment)
On-treatment	Treatment Start Date ≤ Death Date ≤ Treatment Stop Date + 7
Off-treatment	Subjects that prematurely discontinued study treatment that attended the Week 52 visit: Treatment Stop Date + 7 < Death Date ≤ date of Week 52 + 7  Subjects that prematurely discontinued study treatment that withdrew from the study prior to Week 52: Treatment Stop Date + 7 < Death Date ≤ projected Week 52 date + 7
Post-study	Subjects that completed study treatment: Death Date > Treatment Stop Date + 7  Subjects that prematurely discontinued study treatment that attended the Week 52 visit: Death Date > date of Week 52 + 7  Subjects that prematurely discontinued study treatment that withdrew from the study prior to Week 52: Death Date > projected Week 52 date + 7
Note: Study treatment completion is defined in Section 11.5.1.3. The projected Week 52 date is defined in Section 11.5.1.4.	

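### A missing treatment stop date is set to the date of death even for a subject lost or withdrawn earlier, so the death counts as on-treatment and unobserved months count as event-free time on drug

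*SAP*

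**What the plan says.** SAP 11.5.1.2 imputes a missing treatment stop date in two branches. The first applies "If any of Study Treatment Discontinuation Visit date, Visit 7 (Week 52) date, date of death are non-missing"; the stop date is then "the minimum of (Study Treatment Discontinuation Visit date, Visit 7 (Week 52) date, date of death, date that all study treatment containers were returned". A date of death alone is enough to enter this branch. Otherwise: "For all other subjects, the last recorded exposure start or stop date will be used".

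The stop date feeds several other rules:

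- **Mortality phase (SAP 11.3.2).** A death is on-treatment if "Treatment Start Date ≤ Death Date ≤ Treatment Stop Date + 7". For a subject who left the study before Week 52 it is off-treatment if "Treatment Stop Date + 7 < Death Date ≤ projected Week 52 date + 7".
- **Exposure (SAP 11.5.4.1).** Stop minus start plus one day, with no cap.
- **Time to first on-treatment exacerbation (SAP 11.5.3.1).** Event-free subjects are "censored at the earliest of the date of their treatment stop date +1 day or the date of death". SAP 11.5.4.8 has the same rule for time to first safety event.
- **Rate denominator (SAP 11.5.1.5.2).** The minimum of stop plus one day, death and study conclusion.

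For early discontinuers, SAP 11.3.3.1 dates study conclusion at the latest of last phone contact, last clinic visit and the date lost. For subjects lost to follow-up, Protocol 4.5.3 adds: "Every effort should be made to collect survival status". Protocol 4.5.1 seeks the same for subjects who withdraw, where consent allows.

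**The concern.** A subject who disappears without an IP Discontinuation Visit and without returning the inhalers is a natural case for a missing stop date. Because the protocol seeks survival status to the end of the planned 52 weeks, a death well after last contact can be recorded for such a subject. The first branch then has one date to work with, the date of death, and neither last contact nor last dispensing limits it. Exposure therefore depends on what is later learned about vital status.

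What is at stake is the on-treatment label on some deaths, the exposure summaries, and the follow-up counted in the Cox analyses. One of those, time to first moderate/severe exacerbation, is in Block 2 of the testing hierarchy (SAP 11.9). Stretching unobserved time as event-free lowers the apparent hazard for exacerbation, pneumonia and cardiovascular events in whichever arm the subject belongs to.

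**Working it through.** The plan gives no figure to reproduce here, so the check applies the rules as written to constructed records.

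**Assumed record (not from the documents).** Treatment starts on Day 1. Last recorded exposure date is Day 113. The subject is declared lost, and so concludes the study, on Day 170. There is no discontinuation visit, no Visit 7 and no all-containers-returned date. No exacerbation occurred before the loss. Only the date of a later-reported death varies.

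**Formulas (S = imputed stop, in study days).**

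- S = death date if a death is known, otherwise 113 (11.5.1.2).
- Exposure = S − 1 + 1 (11.5.4.1).
- Time-to-first censoring = min(S + 1, death) (11.5.3.1, 11.5.4.8).
- Rate at-risk days = min(S + 1, death, 170) (11.5.1.5.2).
- Projected Week 52 + 7 = 1 + 364 + 7 = Day 372 (11.5.1.4, 11.3.2).

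| Death reported | S | Exposure (days) | Time-to-first censoring (days) | Rate at-risk (days) | Death phase as written |
|---|---|---|---|---|---|
| none known | 113 | 113 | 114 | 114 | – |
| Day 200 | 200 | 200 | 200 | 170 | on-treatment |
| Day 260 | 260 | 260 | 260 | 170 | on-treatment |
| Day 330 | 330 | 330 | 330 | 170 | on-treatment |
| Day 372 | 372 | 372 | 372 | 170 | on-treatment |
| Day 400 | 400 | 400 | 400 | 170 | on-treatment and post-study |

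For the Day 330 death:

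- Exposure is 330 − 113 = 217 days longer than for the identical subject not known dead.
- Time-to-first follow-up is 330 − 114 = 216 days longer.
- The rate denominator is 170 − 114 = 56 days longer.
- The same subject is at risk for 170 days in the rate analysis and for 330 days in the Cox analysis. The Cox sensitivity analysis that adds off-treatment data, which is censored at study conclusion or death, would follow the subject to Day 170 only.

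**With S = 113 instead.** For each death date in the table, exposure is 113 days, and time-to-first censoring and rate at-risk time are both 114 days. Deaths on Days 200 to 372 become off-treatment, because each is later than 113 + 7 = Day 120. The Day 400 death is post-study only.

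**When the problem does not arise.** If all containers came back on Day 150 and death was on Day 330, then S = 150. The death is off-treatment, because 330 > 157.

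**Possible size, on assumptions only.** Suppose 100 to 300 of 10,000 subjects are lost with no stop date, annual mortality is 2% to 4%, and half a year remains. The affected deaths are then 100 × 0.02 × 0.5 = 1 to 300 × 0.04 × 0.5 = 6. Six subjects at 216 extra days each give 1,296 days, or 1,296 / 365.25 ≈ 3.5 subject-years, in a trial planned for 10,000 subjects over 52 weeks.

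**The case against.** The strongest reply is that little depends on this. The primary offset and the adverse event denominators stop at study conclusion. Mortality including off-treatment data counts a death up to projected Week 52 + 7 whichever label it carries. On-treatment mortality is outside the hierarchy. Time to first exacerbation has a sensitivity analysis censored at study conclusion. A stop date may well be recorded for many lost subjects, since Protocol 4.4.4 lists loss to follow-up as a reason for stopping IP. All of this stands and limits the size.

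A second reply is that calling doubtful events on-treatment is the SAP's cautious convention (11.6.1). That convention covers events whose own date is partial or missing. Here the death date is known and the stop date is what is missing. Nor is it cautious for pneumonia or cardiovascular hazards, where added event-free time dilutes risk.

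Some stronger readings are tempting but not supported:

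- **Compliance is diluted by the longer denominator.** SAP 11.5.2.3 sets compliance to missing when any dose counter stop is missing, as it would be for an unreturned inhaler.
- **A phone contact at Visit 7 makes a subject on-treatment for the full year.** Phone follow-up normally comes after the IP Discontinuation Visit, whose earlier date would win the minimum. The route needs that visit, the stop date and the all-containers-returned date all to be absent.
- **The 217 days measure the error against the truth.** Day 113 is the last recorded exposure date, not a known last dose. The figure shows only how far two identical records diverge.
- **The rule favours an arm.** It is the same in all three blinded arms, and nothing in the documents shows that affected subjects would be unevenly spread.

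**Conclusion.** The rule as written gives a wrong result in a case the protocol makes foreseeable. With no recorded stop date, no discontinuation visit, no Visit 7 and no earlier all-containers-returned date, the death date becomes the stop date, and the death is on-treatment whatever the gap since last contact. Time-to-first censoring then runs on through unobserved months, inconsistently with the rate denominator.

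The effect is minor. The number of subjects is not in the documents; 1 to 6 deaths rests wholly on the assumed counts and mortality above. On those figures the extra follow-up is too small to be expected to move the Block 2 hazard ratio. The primary rate is exposed only up to the date the subject is declared lost. The outputs most open to it are on-treatment all-cause mortality, on-treatment adjudicated deaths and the exposure summaries, where a few records can be seen.

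**What to change.** 1. **SAP 11.5.1.2.** Use the date of death only if the subject had not been lost or withdrawn before death. Otherwise use the last recorded exposure date, as for other lost subjects. State which date marks the loss; the study conclusion date defined in 11.3.3.1 would serve.
2. **Do not simply add last recorded exposure to the minimum.** If that date is the dispensing day, Day 113, a subject who dies on drug three weeks later (Day 134) would get a stop of Day 113. The death would fall after Day 120, and a true on-treatment death would become off-treatment.
3. **SAP 11.5.3.1 (on-treatment time to first) and 11.5.4.8.** Add study conclusion to the censoring minimum, as 11.5.1.5.2 already does.
4. **Optional.** Restrict the Visit 7 date in 11.5.1.2 to clinic attendance on IP. This matters only when the stop date and the discontinuation visit are both missing and no all-containers-returned date exists.
5. **Optional.** Report the number of imputed stop dates by arm.

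The cost is a few SAP sentences and minor programming, best settled before unblinding. A few deaths may move from on- to off-treatment.
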